9.2.1 Provider/Site/Patient Selection

Provider Eligibility

Providers who meet the following criteria will be eligible to participate:

- 1) Are board-certified oncologist/hematologist.
- 2) Have treated/are treating at least one eligible patient with an *NRG1* fusion-positive solid tumor.
- 3) Are able to participate in research approved by an external institutional review board (IRB).
- 4) Agree to participate in data quality assurance/control processes.

Providers will select patients meeting the study eligibility criteria as described below. Providers will be asked to select eligible patients chronologically, starting with the first patient who first initiated any line of afatinib or chemotherapy, on or after 01/01/2017 through 03/31/2020.

Patient Eligibility

Inclusion Criteria:

- Adults, 18 years of age or older, at the time of diagnosis with any solid tumor.
- Confirmed *NRG1* gene fusion in any solid tumor.
- Initiated afatinib or other systemic therapy (in any line of therapy) for treatment of a solid tumor with *NRG1* gene fusion on or after 01/01/2017 through 03/31/2020.

- Followed up for ≥ 3 months after initiation of afatinib or other systemic therapy (unless deceased prior to 3 months of follow-up).

Exclusion Criteria:

- Treatment with any TKI/ErbB-directed therapy other than afatinib

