The ORR among patients with *NRG1* gene fusion-positive solid tumors treated with afatinib and among patients with *NRG1* gene fusion-positive solid tumors treated with other systemic therapy will be calculated as the proportion of patients with a complete response (CR) or partial response (PR) out of all patients (CR+PR/all patients) (see **Table 2** below). Disease response for determining the ORR will be reported as recorded in the patient's EHR, including the date of radiographic imaging used to substantiate the patient's initial and best response to therapy. Providers will indicate whether the patient experienced a CR, PR, stable disease (SD), or progressive disease (PD). No independent blinded review of radiology studies will be conducted. Lesion measurements at baseline (initiation of afatinib; initiation of other systemic therapy for non-afatinib treated patients), initial response, and best response will be abstracted as available. Changes in the number, locations, and sizes of lesions at initial and best response to therapy will be evaluated by [REDACTED] using RECIST v1.1 guidelines. The sum of lesion measurements will be assessed at baseline and at follow-up scans to calculate the percent change in sum of target lesions, as well as account for new lesions on follow-up scan in order to classify response by RECIST v1.1 criteria. Actual scan images will not be reviewed; the calculation of real-world disease response will be based on the lesion measurements provided. Other outcomes include PFS, TOT, TTP, OS, DOR, DOCB, AEs. Definitions of these outcomes are shown in **Table 2**.

Table 2. Study outcomes and definitions.

Outcome	Definition
ORR	Proportion of patients with a complete response (CR) or partial response (PR) out of all patients (CR+PR/all patients) at initial response assessment and best response
DOCB	Duration of clinical benefit (DOCB) will be calculated as the time from initial response (for any patient with a complete, partial, or stable disease response initially) until the earliest of either disease progression or death. Patients who discontinue therapy due to a reason other than progression will be censored on the date of discontinuation. Patients still on therapy at the time of data cut-off will be censored on their last visit date.

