9.7 DATA ANALYSIS

Demographic and clinical characteristics will be reported by descriptive analyses including counts and frequencies for dichotomous and categorical variables, while measures of centrality (mean, median) and spread (min, max, standard deviation, interquartile range, as appropriate) will be used for continuous variables. These characteristics will be described at the time of initial diagnosis of advanced/metastatic disease and at the time of initiation of each line of therapy received, for the afatinib cohort and separately for the other systemic therapy cohort. No statistical comparisons will be made across these two cohorts in terms of demographic, clinical characteristics, and clinical outcomes.

The calculations for all outcomes (e.g., ORR, DOR, DOCB, TOT, TTP, PFS, OS) are defined in **Table 2** in Section **9.3.2 Outcomes**. For disease response, the point estimate for ORR and associated 95% confidence interval (CI) will be calculated for initial response to index therapy (i.e., afatinib or other systemic therapy) and best response to index therapy, for each cohort. ORR will be reported among subgroups within each of the treatment cohorts, by tumor type and line of therapy. The Kaplan-Meier method will be used to estimate time-to-event outcomes (DOR, DOCB, TOT, TTP, PFS, and OS) to account for any right-censoring (e.g., patient had not discontinued therapy, patient had not progressed, or died). Time-to-event outcomes will be described for each of the two treatment cohorts and in subgroups within the two treatment cohorts, according to solid tumor and line of therapy. All study outcomes will be reported separately for those treated with afatinib monotherapy. In the event an outcome cannot be assessed for a given patient, that patient would be omitted from assessment of that outcome; reason for omission in a given outcome assessment will be reported.

Cumulative incidence, severity, and timing of AEs during the index therapy will be summarized and displayed in number/percentage form for each of the treatment cohorts, separately. All safety endpoints will be analyzed descriptively. AE reporting is summarized in Section **11 Management and Reporting of Adverse Events/Adverse Reactions**.

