9.3.2 Outcomes? (e.g. International Classification of Diseases (ICD), Medical Dictionary for Regulatory Activities (MedDRA))				9.3.2*
9.3.3 Covariates and other characteristics?				9.3.2*
9.4 Is a linkage method between data sources described? (e.g. based on a unique identifier or other)				

Comments:

*Where applicable

Section 10: Analysis plan	Yes	No	N/A	Section Number
10.1 Are the statistical methods and the reason for their choice described?				9.7
10.2 Is study size and/or statistical precision estimated?				9.5
10.3 Are descriptive analyses included?				9.7
10.4 Are stratified analyses included?				9.7
10.5 Does the plan describe methods for analytic control of confounding?				
10.6 Does the plan describe methods for analytic control of outcome misclassification?				
10.7 Does the plan describe methods for handling missing data?				9.7
10.8 Are relevant sensitivity analyses described?				9.7

Comments:

--

Section 11: Data management and quality control	Yes	No	N/A	Section Number
11.1 Does the protocol provide information on data storage? (e.g. software and IT environment, database maintenance and anti-fraud protection, archiving)				9.6

Section 11: Data management and quality control	Yes	No	N/A	Section Number
11.2 Are methods of quality assurance described?				9.8

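### The omission rule in section 9.7 conflicts with the all-patients definition of ORR and, if applied, raises ORR above that definition

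*Combined protocol and SAP*

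**What the plan says.** Section 9.3.2 defines ORR twice, in the text and in Table 2, with the same denominator: "out of all patients (CR+PR/all patients) at initial response assessment and best response". Section 9.7 adopts that definition: "The calculations for all outcomes (e.g., ORR, DOR, DOCB, TOT, TTP, PFS, OS) are defined in" Table 2.

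The same paragraph of 9.7 ends with a general rule: "In the event an outcome cannot be assessed for a given patient, that patient would be omitted from assessment of that outcome". It adds that reasons for omission will be reported. It does not say when an outcome counts as not assessable, and it exempts no outcome.

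Other parts of the plan that bear on this:

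- Section 9.3.2, response categories: "Providers will indicate whether the patient experienced a CR, PR, stable disease (SD), or progressive disease (PD"). No category for a patient who was not assessed is named there.
- Section 9.3.2, lesion measurements: those at baseline, "initial response, and best response will be abstracted as available".
- Section 9.4: only the eligibility items are required data; anything else may be missing.
- Section 9.2.1: three months of follow-up is required "unless deceased prior to 3 months of follow-up". The abstract says early deaths are kept eligible in order to avoid bias.
- Section 9.7, subgroups: "ORR will be reported among subgroups within each of the treatment cohorts, by tumor type and line of therapy".
- Annex 2, checklist Section 10: "10.7 Does the plan describe methods for handling missing data" is answered yes, citing 9.7. Apart from Kaplan-Meier censoring, the omission sentence is the only rule for missing outcome data in that section.

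**The concern.** One endpoint has two denominators and no order of priority. Under Table 2, a patient who dies before any response assessment stays in the denominator as a non-responder. Under the omission sentence, that patient drops out. For ORR, this would undo the protection gained by keeping early deaths eligible.

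The sentence cannot simply be read as meant for other outcomes. The time-to-event outcomes already have censoring rules in Table 2, and DOR and DOCB are restricted by definition to patients with a qualifying initial response. ORR is therefore a natural target for it.

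No between-cohort comparison is planned, so each cohort's own ORR and confidence interval carry the response evidence. Section 7 says the data may support label-expansion requests. With both rules on file, the denominator could be settled after the data are seen. Initial-response ORR, best-response ORR and the subgroup ORRs could also end up with different denominators.

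**Working it through.** **Inputs from the plan.** Cohort sizes are up to 70 (afatinib) and up to 50 (other systemic therapy), from sections 9.1 and 9.5. Table 4 gives ±10.7% for n = 70 at a proportion of 30%. The plan states no expected ORR and no non-assessed share, so it has no ORR figure to reproduce, and every count below is an assumption.

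**Check of the Table 4 yardstick.** 1.96 × √(0.30 × 0.70 / 70) = 10.7%. The entry reproduces as a 95% half-width, although the table labels it a standard error. It is used here as a half-width.

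**Formula.** Let k be the recorded responders, N all patients in the cohort, and m the patients omitted. An omitted patient has no recorded CR or PR, so k is the same under both rules.

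- Defined ORR = k/N
- ORR under the omission rule = k/(N−m)
- Ratio = N/(N−m), which exceeds 1 whenever m ≥ 1; the ORR itself rises if k ≥ 1

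**Afatinib cohort, N = 70, k = 21 (exact Clopper-Pearson 95% CIs).**

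| Omitted m | ORR | 95% CI | Factor N/(N−m) | Shift (points) | Shift ÷ 10.7 |
|---|---|---|---|---|---|
| 0 | 21/70 = 30.0% | 19.6–42.1 | 1 | 0 | 0 |
| 3 | 21/67 = 31.3% | 20.6–43.8 | 1.045 | 1.3 | 13% |
| 7 | 21/63 = 33.3% | 22.0–46.3 | 1.111 | 3.3 | 31% |
| 14 | 21/56 = 37.5% | 24.9–51.5 | 1.250 | 7.5 | 70% |

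**Other response rates, N = 70, m = 3, 7, 14.** With k = 14, 20.0% becomes 20.9, 22.2 and 25.0%. With k = 28, 40.0% becomes 41.8, 44.4 and 50.0%.

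**Other systemic therapy cohort, N = 50, k = 15.** 30.0% (17.9–44.6) becomes 33.3% (20.0–49.0) with 5 omitted and 37.5% (22.7–54.2) with 10 omitted.

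**Assumed subgroup of 10, k = 3.** 30.0% (6.7–65.2) becomes 33.3% (7.5–70.1) with 1 omitted and 37.5% (8.5–75.5) with 2. One or two patients move a subgroup figure as far as 7 or 14 move the whole cohort.

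**The opposite error.** If some true responders were assessed but their response was not charted, counting them as non-responders lowers the all-patients ORR by 1/70 = 1.4 points each. With 21 true responders:

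- 1 uncharted: 20/70 = 28.6% (18.4–40.6)
- 2 uncharted: 19/70 = 27.1% (17.2–39.1)
- 3 uncharted: 18/70 = 25.7% (16.0–37.6)

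**The case against.** The strongest reply is that Table 2 governs. The all-patients denominator is stated twice, 9.7 defers to it by name, and a specific definition normally overrides a general clause. That is a reasonable reading, but no text says so, and an analyst who applied the omission sentence to ORR would also be following 9.7.

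Second, reasons for omission will be reported, so a reader who also has the cohort size and responder count could usually recover the defined ORR. This helps transparency. It does not correct the headline estimate or its interval.

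Third, the study is descriptive, with no hypothesis and no success threshold. That lowers the stakes, but a descriptive estimate should still match its own definition.

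Fourth, the upward direction is relative to recorded responses over all patients, not to the true response rate. This stands. If 7 omitted patients included 2 uncharted responders out of 21 true ones, the omission rule would give 19/63 = 30.2%, close to the true 30.0%, while the all-patients figure would be 27.1%. The net bias against the truth depends on how many unassessed patients were never assessed and how many were assessed but not charted. The plan does not separate the two.

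Two limits also stand. The eCRF is not in the documents, so it may already have a not-assessed option. And an early death need not be unassessed, since progression may have been recorded first.

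**Conclusion.** The concern holds. Section 9.7 contains a rule that, followed literally, contradicts the ORR definition the same section adopts, and nothing in the plan resolves the conflict.

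If the rule is applied to ORR, the reported figure exceeds the defined one by the factor N/(N−m) whenever at least one patient is omitted and at least one responds. This is certain relative to the definition; the direction relative to the true response rate is not. The size cannot be known from the documents. At an assumed 30% ORR in 70 patients, the shift is 1.3 points with 3 omitted and 7.5 points with 14. The wording should be settled before any response data are seen.

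**What to change.** Amend 9.7 as follows:

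- State that the omission rule does not apply to ORR. At initial and best response, overall and in subgroups, the main ORR keeps every cohort or subgroup patient in the denominator, and a patient with no recorded CR or PR counts as a non-responder.
- Report the number of not-evaluable patients by cohort and reason, separating those never assessed (including early deaths without an assessment) from those assessed whose response or lesion measurements were not charted.
- Give evaluable-only ORR as a labelled sensitivity analysis.
- The plan does not clearly set up a separate ORR from the RECIST classification of abstracted measurements. If one is reported, use the same all-patients denominator for its main figure. Show the version without scanned-but-uncharted patients only as a sensitivity analysis, because counting them as non-responders may bias that figure downward.

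The cost is two or three sentences, a not-evaluable row by reason in each ORR table, and one sensitivity line. If the eCRF does not already distinguish never assessed from assessed but not charted, it needs one more item. The reported ORR may be lower than under omission, and it will be conservative where a response was assessed but not charted.

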DOR	Duration of response will be calculated as the time from initial response (for any patient with a complete or partial response initially) until the earliest of either disease progression or death. Patients who discontinue therapy due to a reason other than progression will be censored on the date of discontinuation. Patients still on therapy at the time of data cut-off will be censored on their last visit date.
TOT	Time from initiation of a line of therapy until discontinuation for any reason; patients on therapy at the time of data cut-off will be censored on the last date of treatment.
TTP	Time from initiation of a line of therapy until discontinuation due to disease progression; patients on therapy or those who discontinued due to a reason other than disease progression will be censored on the last date of treatment.

PFS	Time from initiation of a line of therapy until disease progression or death; patients on therapy at the time of data cut-off will be censored on the last date of treatment. Patients who discontinue a line of therapy for a reason other than disease progression but who subsequently die prior to the receipt of any other therapy will be considered an event on the date of death.
OS	Time from initiation of any therapy in the metastatic setting until death; patients alive at the time of data cut-off will be censored on the last date the patient was seen by the provider/clinic.
AE	An adverse event is defined as any untoward medical occurrence in a patient administered a medicinal product and which does not necessarily have a causal relationship with this treatment. AEs from a prepopulated list (including “other, please specify”) during each line of therapy will be indicated by providers. The number and proportion of patients experiencing each AE reported during afatinib or other systemic therapy will be reported. See Section 11.1 and Table 3 for further details.

In addition to TOT, to further characterize treatment patterns for those treated with afatinib and those treated with other systemic therapy, the following will be collected (and calculated based on the collected data):

- Treatment history (i.e., regimens, duration, number of cycles, sequence)
- Starting dose of afatinib or other systemic therapy
- Dose modifications of afatinib or other systemic therapy (i.e., dose reductions and their timing, dose increases and their timing, dose delays and their duration and timing)

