9.4 DATA SOURCES

All study data will be entered by the investigators into the eCRF. The eCRF captures data for each of the study variables described in **Section 9.3 - Variables**. The eCRF is designed to allow providers to efficiently move through the patient chart or EMR based on the journey of the patient through the course of disease. The eCRF conforms to the rules and regulations of the Health Insurance Portability and Accountability Act (HIPAA) of 1996 governing the abstraction and storage of protected health information (PHI).

De-identified, patient-level data will be obtained from providers in the [REDACTED] [REDACTED] who will complete an electronic case report form (eCRF) for eligible patients. [REDACTED]

[REDACTED] will recruit providers from [REDACTED] to participate. [REDACTED] is a community of over 7,000 oncologists, hematologists and urologists from across the U.S., with varying levels of time in practice, from practices both within and outside of group purchasing organizations. A subset of this group (~800) participates in retrospective observational research studies. All provider participation in the study is voluntary.

To be eligible to participate, providers must have treated at least one patient meeting the study eligibility criteria, be able to participate in research approved by an external institutional review board (IRB), and agree to participate in data quality control processes. No provider at practices that require local IRB approval at the practice will be eligible to participate. A waiver of obtaining patient consent will be sought for the study. No protected health information (PHI) beyond dates of diagnosis, treatments, and outcomes will be collected.

Providers will abstract demographic-, clinical-, and treatment- related data as available from the patient's electronic health record (EHR), starting from the time of primary malignancy diagnosis through the last date of follow-up with the patient or death. Providers will complete an eCRF for all eligible patients and will begin data abstraction beginning with the first eligible patients and select consecutive patients moving forward in time. Data elements that are required are specified in the study inclusion/exclusion criteria; non-required data elements may be missing/unknown. Providers may abstract data into the eCRF for both patients they personally managed/treated or those managed/treated by other providers within their practice.

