10 PROTECTION OF HUMAN SUBJECTS

Individual patient medical information obtained as a result of this study is considered confidential and disclosure to third parties is prohibited. All study materials including the research protocol and paper-version of the eCRF will be reviewed by a central IRB prior to any data abstraction including field-testing of the eCRF. A waiver of HIPAA authorization for use of PHI will be requested from the IRB since the following three requirements will be met:

1. The use or disclosure of the PHI involves no more than minimal risk to the individuals, based on the following elements:
 - a. An adequate plan to protect identifiers from improper use and disclosure;
 - b. An adequate plan to destroy the identifiers at the earliest opportunity consistent with conduct of the research (unless there is a health or research justification for retaining the identifiers, or such retention is otherwise required by law); and
 - c. Adequate written assurances that the PHI will not be reused or redislosed to any other person or entity, except as required by law, for authorized oversight of the research project, or for other research for which the use or disclosure of PHI would be permitted by HIPAA.
2. The research could not be practicably conducted without access to and use of the PHI; and
3. The research could not practicably be conducted without the waiver.

Providers are required to be able to participate in research covered by a central IRB. At all times, patients' PHI will be kept confidential in accordance with HIPAA. The eCRF will not capture any data related to the patient's name, full date of birth, social security number, health insurance plan number, medical record number, or other such PHI. However, date of disease diagnosis, date(s) of treatment(s) administered (including dates of dose changes), date of the development of health states of interest (i.e., SAEs/FAEs, disease progression), and date of death (if available) will be collected in the eCRF. These items are considered PHI under HIPAA. All study results will be reported in aggregate; however, an anonymized patient-level dataset will be delivered to BI at the completion of the analytic cohort build.

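### The Section 9.7 omission rule has no exemption for known but undated events, so it can selectively drop deaths and bias Kaplan-Meier OS, and plausibly PFS, upward

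*Combined protocol and SAP*

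**What the plan says.** Section 9.7 (Data analysis) specifies Kaplan-Meier for DOR, DOCB, TOT, TTP, PFS and OS, and then, in the same paragraph: "In the event an outcome cannot be assessed for a given patient, that patient would be omitted from assessment of that outcome". It adds that the "reason for omission in a given outcome assessment will be reported". It does not define when an outcome counts as not assessable, and it gives no rule for missing or partial event dates.

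Other sections allow for missing dates. Section 9.4 says "Data elements that are required are specified in the study inclusion/exclusion criteria", and that "non-required data elements may be missing/unknown"; dates of death and progression are not eligibility items. Section 10 says "date of death (if available) will be collected in the eCRF".

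Table 2 (Section 9.3.2) sets the dates each outcome needs:

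- **OS** ends at death; otherwise "patients alive at the time of data cut-off will be censored on the last date the patient was seen by the provider/clinic".
- **PFS** is "Time from initiation of a line of therapy until disease progression or death", with patients still on therapy censored at the last treatment date.
- **TTP** is "Time from initiation of a line of therapy until discontinuation due to disease progression", so its event date is a discontinuation date.
- **DOR and DOCB** start at the initial response, so every patient in them needs a response date.

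Section 9.2.1 requires at least 3 months of follow-up unless the patient died sooner.

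**The concern.** No event time can be computed for a patient known to have died on an unknown date. Under Section 9.7 the natural reading is that this patient leaves the OS analysis. A living patient needs only the date last seen, and the 3-month criterion means that almost every living patient has a recorded contact. Whether a patient is analysed can then depend on whether the patient died.

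Kaplan-Meier handles right-censoring that is unrelated to prognosis. It does not repair deletion of events. The same mechanism is plausible for PFS, though less secure, because the PFS censoring date is the last treatment date, which the follow-up criterion does not guarantee.

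The background section says the results may support applications for label expansion. Cohorts are capped at about 70 and 50 and are split further by tumor type and line of therapy, so losing a few deaths can matter in a subgroup.

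**Working it through.** The documents give no expected OS or PFS and no share of undated events, so there is no planned figure to reproduce. The check is of direction and size under stated assumptions.

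**Mechanism.** Suppose a fraction f of events is deleted at random and all event-free patients are kept. Let p(t) be the chance that a patient at risk at time t has the event observed before censoring. The hazard seen by Kaplan-Meier is then the true hazard multiplied by

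(1 − f) / (1 − f·p(t)).

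Without censoring p = 1, the factor is 1 and there is no bias. The lower p is (more censoring), the larger the upward bias.

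**Hand check.** Take a true median of 12 months and censoring uniform on 3 to 42 months (assumed; Section 9.1 gives a maximum follow-up of about 39 months). About 66.5% of patients then have an observed event, so at time zero:

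- f = 0.10: 0.90 / (1 − 0.0665) = 0.964, and 12 / 0.964 ≈ 12.4 months.
- f = 0.20: 0.80 / (1 − 0.133) = 0.923, and 12 / 0.923 ≈ 13.0 months.

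p(t) falls over time under this censoring pattern, so the full curve should shift a little more than this.

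**Simulation.** 400,000 patients, exponential times, same censoring. Kaplan-Meier medians in months:

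| Omission | True 6 | True 12 | True 24 |
|---|---|---|---|
| None | 6.0 | 12.0 | 23.9 |
| 10% of events, at random | 6.1 | 12.6 | 25.8 |
| 20% of events, at random | 6.3 | 13.3 | 28.1 |
| Same share of event and event-free patients | 6.0 | 12.0 | 23.9 |
| 10% of event-free patients only | 5.9 | 11.5 | 22.3 |
| 20% of all events, taken only from the later half | 4.6 | 11.5 | 29.4 |

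The share of patients with an observed event is 85%, 67% and 45% for the three medians.

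**Second censoring pattern.** Censoring is the earlier of uniform 6 to 45 months and an exponential loss time with mean 36 months.

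- True 12-month median, events deleted at random: 12.7 (10%) and 13.5 (20%). Survival at 24 months goes from 25% to 27% and 30%.
- Only deaths after month 3 can be undated, or event-free patients are also lost at half the rate: 12.3 to 12.4 at 10% and about 12.8 at 20%. The upward shift shrinks but remains.
- True PFS median about 5.5 months, random deletion: about 5.7 (10%) and 5.9 (20%). If only events after month 3 are undated, the median falls to about 5.4 and 5.2, because deleting late events also removes those patients from the early risk set.

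**Imputation check.** Same pattern, true OS median 12 months, 20% undated. Placing the death midway between last contact and the abstraction date gives about 14.3 months, against 13.5 under omission. That midpoint is worse than the rule it would replace.

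**The case against.** Section 9.7 never says that undated events are dropped. That is an inference from an undefined term, and the reasons for omission will be reported, so any loss would be visible. This stands as a point about wording. But omission is the only missing-data rule given, and reporting reasons discloses the loss without correcting the estimate.

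A reader might infer that event-free patients always stay in. The documents do not support this: last-seen and last-treatment dates are not listed as required either, and equal loss on both sides gives no bias. What the 3-month criterion supports is that living patients nearly always have a usable date for OS.

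A reader might also infer that every time-to-event outcome is biased upward. TTP ends at discontinuation, so it does not need a progression or death date. DOR needs a response date from every responder, which makes the loss less one-sided. Nor is the direction certain, as the later-event scenarios show.

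Loss to other centres, conceded in Section 9.9, mostly produces unknown events that are censored, which is a different problem. There are also collection safeguards: Sections 9.1 and 9.2 plan to collect dates of progression and death, Section 9.3.2 has the death date abstracted when death is the reason for stopping therapy, and Section 9.8.2 adds date checks and clinical review. These reduce the number of undated events. They do not cover deaths after treatment ends when the date is unavailable, and forced responses apply only to required questions.

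Finally, the study is descriptive. With 70 patients and a true median of 12 months, about 95% of simulated medians lie between 8 and 18 months, so a shift of 0.6 month is small beside sampling error. That limits the severity. It does not justify a rule that can add bias at no gain.

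**Conclusion.** The point holds for OS and plausibly for PFS. As written, the rule can delete known events while keeping most event-free patients. For a true 12-month median the shift is about +0.6 to +0.7 month with 10% of deaths undated and +1.3 to +1.5 with 20%, assuming exponential times, dates missing at random and event-free patients kept. It grows with the share of patients censored and vanishes without censoring or with equal loss. For short PFS medians it is small and can reverse.

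The real undated share is unknown, so the conclusion is that the estimates may be biased, not that they are. TTP is not affected in this way, and the case for DOR is weaker. The ENCePP checklist points to Section 9.7 for both missing-data methods and sensitivity analyses, but that section contains only the omission sentence for the first and nothing for the second. Severity: should fix.

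**What to change.** In Section 9.7, exempt OS and PFS, and the end date of DOR and DOCB, from the omission rule. Keep each patient with a known but undated event and treat the event as interval-censored between the last contact known to be event-free and the earliest later anchor: start of the next therapy, death, or the abstraction date. Add sensitivity analyses that place the event at each end of the interval. Do not use the midpoint to the abstraction date as the main analysis.

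In the eCRF, make vital status, death date, progression status and date, and last-contact date required fields, accepting month and year and an explicit unknown option. Report the number of undated events per cohort and outcome.

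The cost is a few sentences in Section 9.7, field settings before launch, and a little more analysis work. No extra patients are needed. Estimates may become slightly less favourable, and the late bound can be wide where the abstraction date is the only anchor.
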